All subjects will be assigned a study number that is not linked to their personal identifiers to prevent loss of confidentiality. The number will be the IRB Protocol Number followed by a sequentially number starting with number 01. For example, the first subject enrolled will be assigned study subject number 072012-036-01; the next will be 072012-036-02, and so forth. This number will be assigned by the Clinical Research Manager (CRM) upon confirmation of subject eligibility during the subject registration process. Subject registration will be confirmed once the following documents have been received by the CRM:

- Signed copy of the Informed Consent signature page
- Inclusion/Exclusion worksheet signed by the coordinator and treating physician

XII. Subject Registration

All study subjects must be entered into the Velos database in a timely manner after obtaining the informed consent of the subject. Following completion of baseline assessments and confirmation of subject eligibility, patients will be registered and assigned a subject identification number by the CRM, Subject registration will be confirmed (within 24 hours) once the following documents have been received by the CRM:

- Signed copy of the Informed Consent signature page
 - Inclusion/Exclusion worksheet signed by the coordinator and treating physician
- Since this is a double arm, pilot study, randomization to different treatment arms is not required.

XIII. Study Procedures and Treatment Plan

A. Screening Evaluations (for both treatment and control arms)

The following Screening assessments must be performed within 28 days before the first treatment of study drug:

1. Signed Informed Consent
2. Complete medical history (Med Hx), including documentation of current medications (CM), and Adverse Event (AE) assessment;
3. ECOG Performance Status
4. Complete Physical Examination (PE);
5. Vital Signs - BP, HR, RR, and Temp (°C)
6. Height (cm) and Weight (kg) (Record on weight log – see Appendix 2);
7. Laboratory requirements:
 - Hematology: CBC with differential and platelets
 - Serum Chemistry: Na, K, CL, Ca, CO₂, glucose, BUN, creatinine, AST, ALT, alkaline phosphatase, total bilirubin, total protein, albumin
 - Serum pregnancy test (women <60 years only)
8. Pathology report confirming adenocarcinoma histology
9. Staging work-up:
 - a. Posterior to anterior (PA) and lateral (LAT) chest x ray (unless CT chest done)

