 - Glucose tolerance test (0 hr baseline and 2 hr post ingestion)
 - Insulin level (0 hr baseline and 2 hr post ingestion)
 - Adiponectin (0 hr baseline)

- MCP-1 level (0 hr baseline)
- FACT-Hep Questionnaire
- Disease Assessment
- Chest x-ray or CT scan of the chest
- CT scan of the abdomen and pelvis
- Review of Patient Pill Diary
- MRI Abdomen non-contrast (research study) (UT Southwestern and PHHS patients ONLY)

Early-Term or End of treatment visit (ET/EOT) (Early-Term, if patient discontinues treatment before 8 weeks for any reason) (+/-7 days)

- Complete physical examination
- Vital Signs - BP, HR, RR, and Temp (°C)
- Weight (kg on weight log)
- ECOG Performance Status e
- AE/Toxicity assessment
- Laboratory assessments:
 - Hematology: CBC with differential and platelet count
 - Serum chemistry: Na, K, Cl, Ca, bicarbonate, BUN, creatinine, AST, ALT, alkaline phosphatase, total bilirubin, total protein, albumin
 - CA19-9
 - C-reactive protein level
 - Serum fasting glucose (fasting for at least 8 hours)
- Exploratory Research Lab Evaluations
 - Glucose tolerance test (0 hr baseline and 2 hr post ingestion)
 - Insulin level (0 hr baseline and 2 hr post ingestion)
 - Adiponectin (0 hr baseline)
 - MCP-1 level (0 hr baseline)
- FACT-Hep Questionnaire
- MRI Abdomen non-contrast (research study) (UT Southwestern and PHHS patients ONLY)

Follow up (2 weeks after completing treatment or last treatment date if Early-term (ET)) (+/- 7 days) (this corresponds to week 10 of control arm patients)

- Complete physical examination
- Vital Signs - BP, HR, RR, and Temp (°C)
- Weight (kg, record on weight log)
- ECOG Performance Status
- Laboratory assessments:
 - Hematology: CBC with differential and platelet count
 - Serum chemistry: Na, K, Cl, Ca, bicarbonate, BUN, creatinine, AST, ALT, alkaline phosphatase, total bilirubin, total protein, albumin
 - CA19-9
 - C-reactive protein level
 - Serum fasting glucose (fasting for at least 8 hours)
- Exploratory Research Lab Evaluations
 - Glucose tolerance test (0 hr baseline and 2 hr post ingestion)
 - Insulin level (0 hr baseline and 2 hr post ingestion)
 - Adiponectin (0 hr baseline)
 - MCP-1 level (0 hr baseline)
- FACT-Hep Questionnaire

- Toxicity/AE assessment

Long term Follow-up

Patient's chart will be reviewed intermittently by the study team to assess:

- Disease status
- Vital status

G. *Imaging Procedures*

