- Chest, abdomen and pelvic CT scans will be performed at the treating physicians' discretion. The respective institution's imaging protocols will be followed. Contrast exams will be preferred if there is no contraindication to contrast.
- Baseline CT Scans will be performed and then again every 8 weeks thereafter until disease progression or 2 years – whichever comes first.
- If CT Scans are performed within four (4) weeks after discontinuing pioglitazone, then they do not have to be repeated if the investigator's deems it unnecessary.
- (UT Southwestern and PHS patients ONLY) MRI Abdomen non-contrast will be performed at the Roger's MRI (Department of Radiology) at baseline (7 days before starting therapy with pioglitazone or within 7 days of starting pioglitazone) and a second scan after the end of treatment at week 8 (to be done within 2 weeks of ending pioglitazone). If a patient is unable to complete 8 weeks of pioglitazone but has completed 6-8 weeks of therapy, a follow up MRI will be ordered (also to be done within 2 weeks of ending pioglitazone)

H. Routine and Exploratory Lab Assessments

- Blood for routine CBC, chemistry will be drawn per the laboratory protocol and performed in the clinical laboratory of the respective institutions. Results will be recorded as reported in the electronic medical record.
- A Standard 75 gram oral glucose tolerance test will be performed and blood collection for glucose levels will be obtained prior to the ingestion of the solution (pre-dose (0 hr) and at 2 hours following ingestion). Insulin levels at 0 hr (fasting at least 8 hours) and 2 hours post ingestion will be used to calculate insulin resistance . Record the date of collection, time of collection, and subject ID, on the blood collection source document for exploratory labs. All samples should be labeled for each time point for each patient per study visit. Specimen labels will be provided to each site for each patient.
- The following exploratory labs will be collected in a serum separator tube and sent to [name] laboratory for evaluation:
 - **Adiponectin Levels** : performed at the UT Southwestern Metabolic core as described previously [1]
 - **Insulin level** at 0 and 2 hours: Analysis will be performed at the UT Southwestern Metabolic Phenotypic core as described previously [1]
 - **Monocyte Chemoattractant Protein-1 (MCP-1)** performed at the MagPix multiplexing matching housed at the UT Southwestern Metabolic Core [2]

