 - **PAI-1** performed at the MagPix multiplexing matching housed at the UT Southwestern Metabolic Core [2]
- Prior to shipment, complete the sample inventory logs for each patient so that specimen chain of custody can be established. Include in each batch shipment copies of; 1) the blood collection source documents for each patient; and 2) copies of each subjects specimen inventory form. Keep originals of these documents in the patient chart. Please see appendix XX, Specimen Processing and Shipment Instructions for further details.

Patients accrued at VA North Texas will have sample collected at the respective sites, frozen at -20 to -80 C and shipped on dry ice in batches to the UTSW Metabolic Core via overnight courier FedEx (FedEx number:370843180) to the following address

[name] Laboratory
 Touchstone Diabetes Center
 Department of Internal Medicine
 The University of Texas Southwestern Medical Center
 [name]
 [name]
 [name]
 [contact]
 [contact]

H. Schedule of Events

Procedures	Screening ¹	Baseline	2-Weeks	4-weeks	6-Weeks	8-Weeks	End of Treatment or Early-Term (EOT/ET)	14 –Day Follow-up ³
Informed Consent	X							
I/E & Medical History	X							
Concomitant Medications Review / AE Assessment	X	X	X	X	X	X		
Physical Exam	X		X	X	X	X	X	X
Height (cm) ² and Weight Measurement (Kg)	X		X	X	X	X	X	X
Performance status (ECOG)	X	X	X	X	X	X	X	X
Hematology ⁴		X	X	X	X	X	X	X
Serum Chemistry ⁵		X	X	X	X	X	X	X
Serum pregnancy test	X	X						
CA 19-9		X		X		X	X	X
C-reactive protein		X	X	X	X	X	X	X
Serum fasting glucose		X		X		X	X	X
Glucose tolerance		X		X		X	X	X
Adiponectin		X	X	X	X	X	X	X
Insulin level		X ⁶	X	X ⁶	X	X ⁶	X	X
2 hour insulin level		X		X		X	X	X
MCP-1		X	X	X	X	X	X	X
Chest x-ray or Chest CT scan	X					X	X ⁷	X
CT scan of abdomen and pelvis	X					X	X ⁷	X
Toxicity Assessment		X	X	X	X	X	X	
FACT-Hep Questionnaire		X		X		X	X	X
MRI abdomen noncontrast		X ⁸					X ¹⁰	

1. Within 28 days before starting pioglitazone/Day 1 for control arm
2. Height performed at screening only
3. Within 14 days after discontinuing pioglitazone/week 8 for control arm

4. Hematology: CBC with differential and platelet count
5. Serum chemistry: Na, K, Cl, Ca, bicarbonate, BUN, creatinine, AST, ALT, alkaline phosphatase, total bilirubin, total protein, albumin
6. To be performed in conjunction with glucose tolerance test at 0 hr baseline and 2 hr post ingestion.
7. Chest x-ray must be posterior to anterior (PA) and lateral (LAT) plain chest x-ray.

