2. The oral glucose tolerance test will be performed on the initial visit and every four weeks, in fasting state (at least 8 hrs). Patients will be asked to drink a standard glucose solution containing 75 g of carbohydrate. Blood glucose will be obtained prior to the ingestion (0 hr baseline) of the solution, and at 120 min (2 hr) following the ingestion. Blood samples are collected for glucose levels.
3. Documentation of weight. We will measure weight every week in all patients receiving pioglitazone. (See Appendix 2)

4. Documentation Eastern Oncology Cooperative Group (ECOG) performance status. We will determine the ECOG performance status every week in all patients receiving pioglitazone. (See Appendix 1)
5. Measurement of changes in symptoms and quality of life using the FACT-Hep Scale, version 4. (See Appendix 4).
6. RECIST Criteria will be used to determine response. At the time of every tumor assessment and at the time of study discontinuation, assignment of response to one of three categories will be made; complete response (CR), partial response (PR) or progressive disease (PD). Evaluation of measurable and non-measurable lesions in relationship to the baseline tumor assessment will be used to determine response as follows.
7. *MRI will quantitate changes in a) intratumoral fat deposition in pancreatic cancer and b) visceral/subcutaneous fat distribution in pancreatic cancer patients treated with pioglitazone in this phase II study. To determine intratumoral fat content, we will use a previously described advanced chemical shift-based gradient-echo MRI technique that measures the proton density fat fraction (PDFF) [21]. In addition, MRI will allow quantitative determination of body fat volume in the abdomen e.g. subcutaneous/visceral adipose tissue (SAT/VAT) depots, which have been shown to have an important role in insulin resistance [22, 23].*

XVII. Response Criteria

Evaluation of Target Measurable Lesions

Complete Response (CR): Disappearance of all target lesions.

Partial Response (PR): At least a 30% decrease in the sum of the longest diameter (LD) of target lesions, taking as reference the baseline sum LD.

Progressive Disease (PD): At least a 20% increase in the sum of the LD of target lesions, taking as reference the smallest sum LD recorded since the treatment started, or the appearance of one or more new lesions.

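### A patient's chest may be imaged by x-ray at one assessment and CT at another, so the unqualified new-lesion rule can create false progression in one order and hide progression in the other

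*Combined protocol and SAP*

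**What the plan says.** All references are to the combined protocol and SAP.

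- **XIII.A, Screening Evaluations (staging work-up):** "Posterior to anterior (PA) and lateral (LAT) chest x ray (unless CT chest done". Abdomen and pelvis are staged by CT with contrast; there is no x-ray option for them.
- **XIII.F, Treatment Evaluations, 8 week visit:** "Chest x-ray or CT scan of the chest", with CT for abdomen and pelvis.
- **Schedule of Events:** one row, "Chest x-ray or Chest CT scan", is marked at screening, 8 weeks, end of treatment or early termination, and the 14-day follow-up.
- **XIII.G, Imaging Procedures, first item:** "Chest, abdomen and pelvic CT scans will be performed at the treating physicians' discretion". Local imaging protocols apply, and contrast is preferred unless contraindicated.
- **XIII.G, second item:** "Baseline CT Scans will be performed and then again every 8 weeks thereafter until disease progression or 2 years". The sentence does not say which body regions it covers.
- **XVII, Response Criteria:** progression is a 20% increase in target-lesion diameters "or the appearance of one or more new lesions". A new lesion is also progression under the non-measurable criteria. Confirmation more than 4 weeks later is required for complete and partial response only.
- **XX.B, Statistical Analysis Plan:** response and progression rates after week 8 are reported with exact 95% intervals. Median time to progression and the 24-month progression-free proportion are reported with 90% intervals, and Cox regression on PFS is exploratory.

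**The concern.** The imaging sections leave the chest method open at each visit, while the response section treats every newly seen lesion alike. Combined, they let the result depend on which test was ordered. The consequence depends on the order:

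- **X-ray at screening, CT at week 8.** A lung lesion that was present throughout but could not be seen on the x-ray is seen for the first time. Under XVII as written it can be scored as a new lesion, and so as progression. No confirmation step would catch this. CT under XIII.G runs until progression, so the false call could also end the scheduled scans that would have shown the lesion to be stable.
- **CT at screening, x-ray at week 8.** A lesion seen at baseline may no longer be visible, and a small new one may not be seen. This can delay or mask progression, or look like a lesion disappearing. A confirmatory assessment by x-ray again would not correct it.

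Enrolment includes metastatic disease (VIII), so chest lesions are plausible. At stake are the week-8 progression rate, objective response, and time to progression or PFS.

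**Working it through.** **1. The plan's own figure.** The only sizing figure is 82% power for the adiponectin change (XX.A): n = 15, difference 0.4, SD 0.5, alpha 0.05. A two-sided one-sample t-test has noncentrality (0.4/0.5) × √15 = 3.10 and power 82.1%, which reproduces the figure. It uses no imaging data, so nothing below alters it.

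**2. The passages side by side.**

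| Question | Text | Answer |
|---|---|---|
| Chest method at screening? | XIII.A; Schedule | X-ray or CT |
| Chest method at week 8? | XIII.F; Schedule | X-ray or CT |
| Must the two match? | XIII.A, F, G; Schedule | Not stated |
| Is baseline and 8-weekly CT required? | XIII.G, second item | Yes, region not named |
| Is a lesion seen only after a method change exempt? | XVII | No exception written |
| Must progression be confirmed? | XVII | Not stated; CR and PR only |

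The second item of XIII.G has two readings. If it includes the chest, it contradicts the x-ray option in XIII.A, XIII.F and the Schedule. If it does not, nothing fixes the chest method. Either way the text needs repair.

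**3. Effect of one false progression.** With 15 treated patients, 1/15 = 6.7 percentage points. Illustrative counts with exact (Clopper-Pearson) 95% intervals:

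- 3/15 = 20.0% (4.3% to 48.1%)
- 4/15 = 26.7% (7.8% to 55.1%)
- 5/15 = 33.3% (11.8% to 61.6%)

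**4. How many there might be.** The documents give neither input, so both are assumptions: m, the share of patients going from x-ray to CT (10% to 50%), and q, the share of those with a chest lesion visible only on CT (5% to 30%).

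Expected false progressions = 15 × m × q. Chance of at least one = 1 − (1 − mq)^15.

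| m | q | Expected | Chance of at least one |
|---|---|---|---|
| 10% | 5% | 15 × 0.005 = 0.08 | 7% |
| 25% | 20% | 15 × 0.05 = 0.75 | 54% |
| 50% | 30% | 15 × 0.15 = 2.25 | 91% |

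These counts lean high for given m and q. They assume that every such lesion is scored as new and that the patient was not progressing elsewhere at the same visit.

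**5. The reverse order.** The documents offer no basis for a number. The direction is towards fewer or later progressions and possibly more apparent responses. The two orders can partly offset each other, so the net bias in a mixed sample cannot be signed in advance.

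**The case against.** The strongest reply has four parts.

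- **The standard is RECIST, and a competent assessor would not call such a lesion new.** That may happen in practice. But the plan names no version, and the criteria it writes out contain no rule on method. So false progression is permitted by the text, not made inevitable by it.
- **XIII.G already requires CT at baseline and every 8 weeks.** Following directly on an item that names chest, abdomen and pelvis, the sentence can be read that way. This stands as a reason not to say that the plan is wholly silent. It turns part of the problem into an inconsistency to be reconciled.
- **Only secondary, descriptive endpoints are touched.** This stands. Response and PFS carry no decision threshold, and the illustrative intervals overlap heavily. Progression is not among the listed reasons for ending treatment in XIV, so a false call does not by rule remove week-8 biomarker data.
- **Near zero cases is plausible.** This also stands; the low end of the range is 0.08.

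A reader might go further and infer that the choice of test biases the comparison of arms. Assignment is discretionary and the trial is open label, so the test ordered could differ by arm. However, the between-arm endpoint in VII concerns serum and MRI measures, and XX.B calls all arm comparison exploratory. No specified comparison rests on chest imaging. Nor do the documents leave contrast wholly open: XIII.G states a preference, and XIII.A specifies contrast for abdomen and pelvis.

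**Conclusion.** The point holds in a limited form. The plan allows the chest method to change within a patient, and its new-lesion rule has no provision for that. X-ray then CT can create false progression. CT then x-ray can mask progression or mimic response; it does not create false progression, although a reader might take any mismatch to do so.

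The reach is the chest only, because abdomen and pelvis are CT at screening and at week 8. The affected results are secondary: week-8 progression rate, objective response, and time to progression or PFS. A reader might infer that the trial's main result is at risk, but the adiponectin endpoint, its 82% power and overall survival do not depend on chest imaging.

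Each false progression shifts the treated-arm rate by 6.7 points. The expected number, about 0.1 to 2, rests wholly on the assumed switching and CT-only lesion rates. The change is still worth making: it is specific and cheap, and it removes a known source of bias from planned analyses with only 15 treated patients.

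**What to change.** 1. **Reconcile the imaging text.** State in XIII.G which body regions the baseline and 8-weekly CT covers, and bring XIII.A, XIII.F and the Schedule of Events into line.
2. **Fix the method within each patient.** In XIII.G, the visit lists and the Schedule, state that each follow-up chest assessment uses the same method as that patient's baseline.
3. **Add a classification rule to XVII.** A chest lesion first seen only after a change of method is not by itself a new lesion for progression. It is judged against any later same-method imaging already planned or done.
4. **Report it.** In XX.B, list all such cases and add a sensitivity summary of progression rate and PFS that counts them as progression.

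The second rule is needed even with the first, because a CT may still be ordered for clinical reasons. The rules should be set before scans are read.

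**Cost.** Protocol and SAP wording. No scan is added as long as the classification relies on imaging already planned or done; requiring a further CT to settle each case would add one. The real downside is that some true chest progressions in patients with an x-ray baseline will be called later, or missed on x-ray.

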1.1.1 Definition

An adverse event is defined as any untoward or unfavorable medical occurrence in a human research study participant, including any abnormal sign (for example, abnormal physical exam or laboratory finding), symptom, clinical event, or disease, that occurs during the subject's participation in the research, whether or not it is considered related to the subject's participation in the research.

Adverse events encompass clinical, physical and psychological harms. Adverse events occur most commonly in the context of biomedical research, although on occasion, they can occur in the context of social and behavioral research. Adverse events may be expected or unexpected.

Severity

Adverse events will be graded by a numerical score according to the defined NCI Common Terminology Criteria for Adverse Events (NCI CTCAE) and version number specified in the protocol. Adverse events not specifically defined in the NCI CTCAE will be scored on the Adverse Event log according to the general guidelines provided by the NCI CTCAE and as outlined below.

- Grade 1: Mild
- Grade 2: Moderate
- Grade 3: Severe or medically significant but not immediately life threatening
- Grade 4: Life threatening consequences
- Grade 5: Death related to the adverse event

Serious Adverse Events

ICH Guideline E2A and the UTSW IRB define serious adverse events as those events, occurring at any dose, which meets any of the following criteria:

- Results in death
- Immediately life-threatening
- Results in inpatient hospitalization or prolongation of existing hospitalization
- Results in persistent or significant disability/incapacity
- Results in a congenital anomaly/birth defect
- Based upon appropriate medical judgment, may jeopardize the subject's health and may require medical or surgical intervention to prevent one of the other outcomes listed in this definition.

Note: A "Serious adverse event" is by definition an event that meets **any** of the above criteria. Serious adverse events may or may not be related to the research project. A serious adverse event determination does not require the event to be related to the research. That is, both events completely unrelated to the condition under study and events that are expected in the context of the condition under study may be serious adverse events, independent of relatedness to the study itself. As examples, a car accident requiring overnight hospitalization would be a serious adverse event for any research participant; likewise, in a study investigating end-stage cancer care, any hospitalization or death would be a serious adverse event, even if the event observed is a primary clinical endpoint of the study.

1.1.2 Unanticipated Problems:

The term “unanticipated problem” is found, but not defined in the regulations for the Protection of Human Subjects at 45 CFR 46, and the FDA regulations at 21 CFR 56. Guidance from the regulatory agencies considers unanticipated problems to include any incident, experience, or outcome that meets **each** of the following criteria:

- unexpected; **and**
- related *or possibly related* to participation in the research; **and**
- suggests that the research *places subjects or others at a greater risk of harm* (including physical, psychological, economic, or social harm) *than was previously known or recognized*.

Follow-up

All adverse events will be followed up according to good medical practices.

